### 3.2.4 Choice of study population

#### Age

Different ages for men and women have been selected as inclusion criteria at enrolment to create similar ‘high risk’ of future cardiovascular events. Furthermore, two age strata will be studied: stratum 1 with patients <65 years and stratum 2 with patients of age 65 years and above. The reason is to ensure that a sufficient number of patients of age 65 years and greater will be studied. Age 65 years was chosen as it represents an accepted regulatory cut-off for elderly age groups in clinical studies. In line with the new FDA CV Guidance ([FDA 2008](#)), this study will include patients with a ‘high risk’ of subsequent cardiovascular events including those with age  $\geq 65$  years. In addition, it is of interest to evaluate efficacy and safety of dapagliflozin in relation to age, with the expectation that the elderly age group may exhibit a trends towards more renal impairment and higher prevalence of co-morbidities in relation to those with age <65 years.

#### HbA1c

The HbA1c inclusion criterion at randomisation was selected to include patients with a wide range of glycaemic control. The lower bound of this interval (ie, 7.0%) reflects the most recent ADA and EASD treatment guidelines ([ADA 2009](#); [Nathan et al 2009](#)). Although other guidelines recommend treatment to lower HbA1c targets, the results of recent studies suggest that these stricter targets may not be appropriate for all patients. The upper limit of this interval (ie, 10.0%) was chosen because insulin is generally the treatment of choice for patients with HbA1c values above this level. Higher HbA1c levels reflect hyperglycaemia which in the long run exposes patients with diabetes to a very high risk of developing micro- and macrovascular complications. The reduction in HbA1c is therefore chosen as a primary efficacy endpoint.

#### History of CV Events

Patients with diabetes and cardiovascular disease continue to have an unmet need for optimal glycaemic control ([ADA 2009](#)). This study will include such patients with a past history of CV events as defined in Section 4.1 because they are at a ‘high risk’ of subsequent cardiovascular events. Studying the efficacy and safety of dapagliflozin in such ‘high risk’ patients is in line with the new FDA CV Safety Guidance ([FDA 2008](#)). Furthermore, it is known that the time from diagnosis of a previous CV event is a factor that affects the risk of recurrent CV events ([Alberts et al 2009](#); [Donahoe et al 2007](#)). In order to balance the risk of future cardiovascular events between treatment arms, patients will be stratified according to time from most recent qualifying CV event (1 year or less versus more than 1 year before enrolment) (see Section 3.1.1.4 and Section 4.1, item 6).

#### Insulin use

T2DM patients may be on existing insulin therapy. In the course of diabetes treatment, insulin can be added to OAD to improve glycaemic control ([ADA 2009](#); [Nathan et al 2006](#); [Nathan et al 2009](#)). In patients with T2DM, insulin therapy has been reported to improve glycaemic control, cause weight gain and risk of hypoglycaemia ([Holman et al 2009](#)). Insulin use may

also indicate advanced disease. Dapagliflozin has been used with insulin in patients with T2DM, both with a reduced insulin dose ([Wilding et al 2009](#)) and an unchanged insulin dose (one study in the Phase III programme).

### **Kidney Function**

Several diabetes drugs, notably metformin and DPP-4 inhibitors, need to have their dose reduced in the presence of renal impairment, as measured indirectly from plasma creatinine levels. As detailed in [Appendix K](#) and Section 5.8, patients treated with metformin will need to discontinue metformin when creatinine clearance falls <60 ml/min or an increase in serum creatinine occurs  $\geq 44 \mu\text{mol/L}$  ( $\geq 0.5 \text{ mg/dL}$ ) above baseline value (confirmed within one week). For patients not on metformin, discontinuation of study drug will occur:

- when creatinine clearance falls <60 ml/min, or
- when in subjects with baseline creatinine  $\geq 123 \mu\text{mol/L}$  ( $\geq 1.4 \text{ mg/dL}$ ) an absolute increase in serum creatinine occurs  $\geq 88 \mu\text{mol/L}$  ( $\geq 1.0 \text{ mg/dL}$ ), or
- when in subjects with baseline creatinine <123  $\mu\text{mol/L}$  (<1.4 mg/dL) an absolute increase in serum creatinine occurs of  $\geq 44 \mu\text{mol/L}$  ( $\geq 0.5 \text{ mg/dL}$ ).

### **Pregnancy or breast-feeding**

Dapagliflozin has not been tested in pregnant women and the risks to embryo, foetus, and infant are unknown. For this reason, women who are pregnant or breastfeeding are excluded and women of childbearing age are instructed to take precautions to avoid becoming pregnant during the study.

### **Other**

The purpose of the majority of the inclusion and exclusion criteria is to limit confounding factors that may complicate the interpretation of the study results (eg, corticosteroid-induced type 2 diabetes, haemoglobinopathies that would interfere with the HbA1c analyses) or to exclude patients whose safety could be compromised by participation in the study.

## **4. PATIENT SELECTION CRITERIA**

Investigator(s) should keep a record, the patient screening log, of patients who entered pre-study screening.

Each patient should meet all of the inclusion criteria and none of the exclusion criteria for this study. Under no circumstances can there be exceptions to this rule.

### **4.1 Inclusion criteria**

For inclusion in the study patients should fulfil the following criteria:

**Inclusion criteria at enrolment (Visit 1) and start of placebo lead-in (Visits 2)**

1. Provision of informed consent prior to any study specific procedures
2. Prior diagnosis of type 2 diabetes
3. Age at enrolment visit
  - Men  $\geq 45$  years old
  - Women  $\geq 50$  years old
4. Anti-hyperglycaemic treatment should have been used uninterrupted on a daily basis for 8 weeks and stable for at least 4 weeks before enrolment and identical to one of the following:
  - Monotherapy or dual combination therapy with oral anti-diabetic drug(s) for example metformin, pioglitazone, sulfonylurea, acarbose, or a DPP-4 inhibitor (saxagliptin, sitagliptin, vildagliptin), except rosiglitazone which is not allowed for at least 8 weeks before enrolment (refer to Section 4.2, exclusion criteria 29), or
  - Insulin therapy in combination with oral anti-hyperglycaemic therapy, or
  - Insulin monotherapy
5. At enrolment:  $7.2\% \leq \text{HbA1c} \leq 10.5\%$  (value from blood sample obtained at screening)
6. Cardiovascular disease (Refer to Note 1), defined as:
  - Prior documented Coronary Heart Disease
    - History of myocardial infarction or
    - History of revascularization, or coronary artery stenosis  $>50\%$ , confirmed with angiography or
    - Abnormal imaging at stress test, compatible with ischemia or prior myocardial infarction (Refer to Note 2), or
  - Prior documented Stroke or TIA, or
  - Prior documented Peripheral Artery Disease (PAD) treated with revascularization (amputation is not accepted)

Note 1: The time from the most recent diagnosis of above mentioned CV diseases is used to stratify patients at randomisation (see Section 3.1.1.4).

Note 2: A myocardial perfusion scan ('imaging') can be obtained following thallium, mIBI, or tetrofosmin administration during an exercise stress test or during the pharmacological equivalent of a stress test (using dipyridamole, adenosine, dobutamine or dopamine administration).

7. Hypertension, defined as follows:
  - Prior physician-made diagnosis of essential hypertension, ie, before screening, or
  - Treatment with two or more anti-hypertensive agents (diuretics, beta blockers, ace-inhibitors, angiotensin receptor blockers, or calcium channel antagonists), with one of the agents started for lowering blood pressure, or
  - Treatment with one anti-hypertensive agent and a past physician recording of a blood pressure exceeding 130/80 mmHg.
8. For patients on anti-hypertensive treatment, the anti-hypertensive treatment should have been used uninterrupted on a daily basis in the last 4 weeks before the enrolment.
9. For Women only:  
Women not of childbearing potential or women of childbearing potential who comply with the following:
  - Use a highly effective method of birth control (see below) to avoid pregnancy throughout the study and for up to 4 weeks after the study
  - Have a negative urine pregnancy test (minimum sensitivity 25 IU/L or equivalent units of HCG) within 72 hours prior to the start of study medication and at each visit

**Definitions:**

**Women of Child Bearing Potential** - Women between menarche and menopause who have not been permanently or surgically sterilized and are capable of procreation.

**Women NOT of Childbearing Potential** - Women who are permanently or surgically sterilized or postmenopausal. Permanent sterilisation includes hysterectomy and/or bilateral oophorectomy and/or bilateral salpingectomy but excludes bilateral tubal occlusion. (Tubal occlusion is considered a highly effective method of birth control but does not absolutely exclude possibility of pregnancy.

The term occlusion refers to both occluding and ligating techniques that do not physically remove the oviducts).

**Post Menopausal Women** - Women will be considered postmenopausal if they are amenorrheic for 12 months without an alternative medical cause. The following age-specific requirements apply:

- Women over 50 years of age would be considered postmenopausal if they have been amenorrheic for 12 months or more following cessation of all exogenous hormonal treatments.

**Highly effective method of birth control** is defined as one that results in a low failure rate (eg, less than 1 percent per year) when used consistently and correctly. The following are considered acceptable methods of contraception: total sexual abstinence; vasectomised sexual partner ; tubal occlusion (ligation) ; intrauterine device; levonorgestrel intra uterine system (eg, Mirina); Etonogestrel implants (eg, Implanon, Norplan ); normal and low dose combined oral contraceptive pills; Norelgestromin/EE transdermal system; intravaginal device (eg, EE and etonogestrel); cerazette (desogestrel).

#### **Inclusion criteria at randomisation (visit 4, laboratory values from visit 3):**

Patients should fulfil inclusion criteria 1 to 9 (listed above) and the following criteria at randomisation:

10. HbA1c  $\geq 7.0\%$  and  $\leq 10.0\%$  at randomisation (value from blood sample obtained at Visit 3).
11. Uninterrupted monotherapy or dual combination therapy of oral diabetes drugs (with or without insulin) for at least 12 weeks before randomisation.
12. Insulin treatment for at least 12 weeks before randomisation, if administered.
13. The dose of anti-hyperglycaemic drugs and the insulin regimen should be stable for 8 weeks before randomisation.
14. For patients on current anti-hypertensive treatment the administration of anti-hypertensive drug(s) should be uninterrupted for 8 weeks before randomisation and dose should be stable for 4 weeks before randomisation.
15. Lipid lowering and/ or anti-platelet treatment should be uninterrupted for 4 weeks before randomisation, if administered.

#### **4.2 Exclusion criteria**

Patients should not enter the study if any of the following exclusion criteria are fulfilled:

**The following criteria apply to the enrolment, placebo lead in and randomisation visits (Visits 1, 2, and 4).**

**Endocrine and metabolic disorders**

1. Diagnosis of Type 1 diabetes mellitus, known diagnosis of MODY or secondary diabetes mellitus
2. Use of 3 or more oral anti-hyperglycaemic drugs with or without insulin
3. History of diabetic ketoacidosis
4. Symptoms of poorly controlled diabetes including, but not limited to, marked polyuria, polydipsia, and/or greater than 10% weight loss during the 3 months prior to enrolment
5. FPG >270 mg/dl (>15 mmol/L) at randomisation (sample will be taken at visit 3)
6. History of bariatric surgery (ie, any surgery to treat obesity; for example, gastric banding or procedures that involve bypassing or transposing sections of the small intestine). History of liposuction is allowed.
7. Diabetes insipidus
8. Thyroid-stimulating hormone (TSH) and free T4 values outside normal range. An abnormal TSH value needs to be followed up with a free T4 test. Patients with abnormal free T4 values will be excluded

**Cardiovascular disorders**

9. Recent Cardiovascular Events in a patient:
  - Acute Coronary Syndrome (ACS) within 2 months prior to enrolment
  - Hospitalization for unstable angina or acute myocardial infarction within 2 months prior to enrolment
  - Acute Stroke or TIA within two months prior to enrolment
  - Less than two months post coronary artery revascularization
10. Congestive heart failure defined as New York Heart Association (NYHA) class IV, unstable or acute congestive heart failure. Note: eligible patients with congestive heart failure, especially those who are on diuretic therapy, should have careful monitoring of their volume status throughout the study.
11. Blood pressure:

- At enrolment (Visit 1):  
Systolic BP  $\geq$ 165 mmHg and/or diastolic BP  $\geq$ 100 mmHg
- At randomisation (Visit 4):  
Systolic BP  $\geq$ 160 mmHg and/or diastolic BP  $\geq$ 100 mmHg

Note: For assessment of this criterion, an average blood pressure should be used, calculated from 3 measurements. At Visit 4 measurements in each of the three positions: sitting, supine, and standing, should be assessed for eligibility (see Section 6.4.8.1).

### **Kidney disorders**

12. Calculated creatinine clearance  $<$ 60 mL/min
13. Urine albumin: creatinine ratio (UACR)  $>$ 1800 mg/g ( $>$ 203.4 mg/mmol/L)
14. History of unstable or rapidly progressing renal disease
15. Familial renal glucosuria. This condition is diagnosed as glucosuria ( $>$ 1.0 mmol/L urine) in the presence of normoglycaemia in a patients without the diagnosis of diabetes mellitus

### **Hepatic disorders**

16. Severe hepatic insufficiency and/or significant abnormal liver function defined as aspartate aminotransferase (AST)  $>$ 3x upper limit of normal (ULN) and/or alanine aminotransferase (ALT)  $>$ 3x ULN
17. Total bilirubin  $>$ 2.0 mg/dL (34.2  $\mu$ mol/L)
18. Positive serologic evidence of current infectious liver disease including Hepatitis B viral antibody IGM, Hepatitis B surface antigen and Hepatitis C virus antibody
19. History of drug-induced liver enzyme elevations
20. History of severe hepatobiliary disease or hepatotoxicity with any medication

### **Hematologic/oncologic disorders/conditions**

21. Haemoglobin  $<$ 10 g/dL ( $<$ 100 g/L) or 6.2 mmol/L for men; haemoglobin  $<$ 9.0 g/dL ( $<$ 90 g/L) or 5.9 mmol/L for women
22. History of chronic haemolytic anaemia or haemoglobinopathies (for example, sickle cell anaemia, thalassemia, sideroblastic anaemia). Mild haemolysis due to artificial heart valves or due to sickle cell trait is not an exclusion criterion except when haemoglobin levels are too low (as defined in haemoglobin criteria above).

23. Donation or transfusion of blood, plasma, or platelets within the past 3 months prior to Visit 1
24. History of malignancy within the last 5 years, excluding successful treatment of basal or squamous cell skin cancer

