### **5.3 Procedures for handling patients incorrectly enrolled or randomised or initiated on investigational product**

Patients who fail to meet the inclusion/exclusion criteria should not, under any circumstances, be enrolled or randomised. There can be no exceptions to this rule.

Patients who are incorrectly enrolled but are not yet randomised should be withdrawn from the study.

Where patients that do not meet the selection criteria are randomised in error or incorrectly started on treatment, or where patients subsequently fail to meet the study criteria post initiation, a discussion should occur between the AstraZeneca Study Delivery Team Physician and the Investigator through local AstraZeneca contact regarding whether to continue or discontinue the patient from treatment.

The AstraZeneca Study Delivery Team Physician is to ensure all such decisions are appropriately documented. In situations where an agreement cannot be reached, the patient should have their study therapy stopped and should be withdrawn from the study.

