**Table 6 Glycaemic Rescue Criteria (24-week double blind treatment period)**

Period	Central Laboratory FPG
From week 0 (Visit 4) to week 4 (Visit 6) including day of Visit 6	FPG >270 mg/dL (15.0 mmol/l)
From week 4 (Visit 6) to week 8 (Visit 7) including day of Visit 7	FPG >240 mg/dL (13.2 mmol/l)
From week 8 (Visit 7) to week 24 (Visit 9) including day of Visit 9	FPG >200 mg/dL (11.1 mmol/l)

If self-monitored FPG is above the upper limit defined for each period as described in [Table 6](#), the patient should repeat the FPG on the same day. If the second result is also above the upper limit defined for each period as described in [Table 6](#), the patient should contact the study centre and will be scheduled for a central laboratory FPG measurement within one week. If the FPG result of the central laboratory is above the upper limit of the treatment period as described in [Table 6](#), the rescue criterion is met and a Rescue Visit will be scheduled within 5 working days to adjust the anti-hyperglycaemic therapy.

**Table 7 Glycaemic Rescue Criterion (28-week site- and patient-blinded treatment period I and 52-week site- and patient-blinded extension period II)**

Period	Central Laboratory HbA1c
From week 24 (Visit 9) to week 52 (Visit 13) including day of Visit 13.	Central Laboratory HbA1c >8.0% (repeated and confirmed)
From week 52 (Visit 13) to week 65 (Visit 14) including day of Visit 14.	Central Laboratory HbA1c >7.5% (repeated and confirmed)
From week 65 (Visit 14) to week 104 (Visit 17) excluding day of Visit 17	Central Laboratory HbA1c >7.0% (repeated and confirmed)

From week 24 (Visit 9) to week 104 (Visit 17), if self-monitored FPG is above 200 mg/dL, the patient should repeat the FPG on the same day. If the second result is also above 200 mg/dL, the patient should contact the study centre and will be scheduled for a central laboratory HbA1c measurement within one week.

Investigators are blinded to patients' HbA1c results throughout the study. However, after Visit 9 (week 24), during the 28-week and the 52-week site- and patient- blinded extension periods, a different glycaemic rescue criterion has been defined for the safety of the patients. From week 24 (Visit 9) to week 52 (Visit 13) patients with a central laboratory HbA1c value

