## Dose Reduction

Dose reduction of daily insulin shall be ordered by the investigator under the following circumstances:

- Within the first 7 days of active randomised treatment, if the patient reports two or more readings of plasma glucose value  $\leq 80$  mg/dL ( $\leq 4.4$  mmol/L).
- After the first 7 days of active randomised treatment, if the patient reports two or more readings of plasma glucose value  $\leq 70$  mg/dL ( $\leq 3.8$  mmol/L). Patients should be encouraged to contact the investigator in such circumstances to allow the reduction of insulin dose.

Changes in concomitant insulin medication must be recorded in the appropriate sections of the eCRF.

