#### Hypoglycaemic events

The patients will be asked to always check their blood glucose if they develop symptoms suggestive of hypoglycaemia and to record specific symptoms in the patient diary.

A hypoglycaemic event can be either:

- Symptoms of hypoglycaemia with a low blood glucose reading
- A low blood glucose reading
- Symptoms of hypoglycaemia without a blood glucose reading

For the evaluation of hypoglycaemic events, this study will use the definitions provided in the CPMP guidance on clinical investigation of medicinal products in the treatment of diabetes mellitus, as described below.

- **Major hypoglycaemic events**, defined as symptomatic events requiring external assistance due to severe impairment in consciousness or behaviour, with a capillary or plasma glucose value <54 mg/dL (<3.0 mmol/L), and prompt recovery after glucose or glucagon administration.

- **Minor hypoglycaemic event**, defined as either a symptomatic event with a capillary or plasma glucose value  $<63$  mg/dL ( $<3.5$  mmol/L) but  $>54$  mg/dL ( $3.0$  mmol/L), and no need for external assistance, or an asymptomatic blood glucose measurement  $<63$  mg/dL ( $<3.5$  mmol/L).
- **Events suggestive of hypoglycaemia**, defined as a symptomatic event without a confirmatory blood glucose measurement.

If the patient experiences symptoms suggestive of hypoglycaemia and has an associated capillary or plasma glucose value  $\geq 63$  mg/dL ( $\geq 3.5$  mmol/L), the event should be recorded as an adverse event rather than as a hypoglycaemic event. If the physician does not consider the glucose measurement to be accurate, however, the event should be documented as a hypoglycaemic event in the hypoglycaemia eCRF.

Data to be collected for each hypoglycaemic event:

- Date and time of episode (start and stop)
- Whether the patient was sleeping at the time of the event
- Whether symptoms were present, and list of symptoms
- Possible contributing factors
- Whether a fingerstick value was obtained, and if so, the plasma glucose value
- Whether intervention was needed for recovery
- How the episode was treated
- Whether recovery was prompt after treatment
- Time of last anti-hyperglycaemic drug administration
- Time of last meal

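### The women's haemoglobin limit in exclusion 21 is wrong in mmol/L (5.9 should be 5.6); two glucose limits need small conversion corrections and two rescue rules need wording alignment

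*Supplement*

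**What the plan says.** **Haemoglobin.** Exclusion criterion 21 in Section 4.2 gives each limit in three units. Men: below 10 g/dL (100 g/L) "or 6.2 mmol/L for men". Women: below 9.0 g/dL (90 g/L) "or 5.9 mmol/L for women". Exclusion 22 refers back to these limits. Section 5.3 leaves no latitude: "Patients who fail to meet the inclusion/exclusion criteria should not, under any circumstances, be enrolled or randomised".

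**Glucose.** Table 6 (Section 5.6.2.1) sets the weeks 4 to 8 rescue limit as "FPG >240 mg/dL (13.2 mmol/l)" and the weeks 8 to 24 limit as "FPG >200 mg/dL (11.1 mmol/l)". Other pairs are in exclusion 5, "FPG >270 mg/dl (>15 mmol/L) at randomisation", and in the definition of a major hypoglycaemic event in Section 6.4.9.1, "plasma glucose value <54 mg/dL (<3.0 mmol/L)". The insulin dose-reduction rule in Section 5.6.2.2 begins "After the first 7 days of active randomised treatment, if the patient reports two or more readings of plasma glucose value" and sets the limit at 70 mg/dL or less, with 3.8 mmol/L as the equivalent.

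**Operators.** Section 5.6.2.4, paragraphs A and B, opens by permitting a change of antihypertensive therapy when pressure is strictly above 160/100 (A) or 140/95 (B). The sentences that trigger the return visit and the added treatment use the inclusive limits, ≥160/≥100 and ≥140/≥95. For the extension, Table 7 sets HbA1c rescue strictly above the level, while the text below it lets a repeat value equal to the level trigger rescue.

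**The concern.** A limit stated in several units has to be the same limit in each. In exclusion 21 the women's g/dL and g/L figures agree with each other and the mmol/L figure does not. The gap is about 0.5 g/dL, too large for rounding, and it sits in an eligibility rule, so one blood result can lead to opposite decisions depending on the unit read.

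The glucose figures are also action limits (rescue therapy and insulin reduction), but the gaps are about 2 and 1.5 mg/dL.

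The mixed operators matter only for a value exactly at the cut-off. They are worth noting because Section 11.1.3 makes a patient rescued for glycaemia or blood pressure before week 24 a non-responder on the 3-item co-primary endpoint, so a boundary case could change status.

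**Working it through.** **1. Haemoglobin.** Inputs: both pairs from exclusion 21. The men's pair gives the conversion factor.

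- Factor: 6.2 / 10 = 0.62 mmol/L per g/dL. As 6.2 is rounded, the factor may lie from 0.615 to 0.625.
- Women: 9.0 × 0.62 = 5.58, so 5.6 mmol/L. Over the rounding range: 9.0 × 0.615 = 5.54 to 9.0 × 0.625 = 5.63.
- The stated figure converted back: 5.9 / 0.62 = 9.52 g/dL (5.9 / 0.625 = 9.44 to 5.9 / 0.615 = 9.59).

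The stated 5.9 cannot be reproduced with any factor that turns 10 g/dL into 6.2 mmol/L. The usual factor of 0.6206 (an assumption from outside the documents) gives the same answer: 5.59 mmol/L, and 9.51 g/dL for 5.9.

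**2. Glucose.** Inputs: the protocol's other pairs, 270/15.0, 200/11.1, 80/4.4, 63/3.5 and 54/3.0. Allowing for rounding, they jointly bound the factor between 80 / 4.45 = 17.98 and 270 / 14.95 = 18.06 mg/dL per mmol/L. With 18:

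| mg/dL | Stated mmol/L | Recomputed | Over 17.98 to 18.06 |
|---|---|---|---|
| 270 | 15.0 | 15.00 | reproduces |
| 240 | 13.2 | 13.33 | 13.29 to 13.35 |
| 200 | 11.1 | 11.11 | reproduces |
| 80 | 4.4 | 4.44 | reproduces |
| 70 | 3.8 | 3.89 | 3.88 to 3.89 |
| 63 | 3.5 | 3.50 | reproduces |
| 54 | 3.0 | 3.00 | reproduces |

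Converted back, 13.2 × 18 = 237.6 mg/dL and 3.8 × 18 = 68.4 mg/dL. Truncation could explain 3.8; it cannot explain 13.2.

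**3. How many patients lie in the gaps.** The documents give no haemoglobin or FPG distribution, so these are normal distributions over assumed ranges.

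- Haemoglobin in women between 9.0 and 9.51 g/dL: 0.012% (mean 13.5, SD 1.1) to 1.3% (mean 12.5, SD 1.5). If 300 to 1,000 women are tested at Visit 1, that is 300 × 0.00012 = 0.04 to 1,000 × 0.013 = 13 women.
- FPG between 237.8 and 240 mg/dL: 0.04% (mean 150, SD 30) to 0.9% (mean 180, SD 50).

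**4. Operators, side by side.** In Section 5.6.2.4 A and B, the sentence that opens the permission is strict; the two sentences that set an action are inclusive. The inclusive form also matches exclusion 11 at randomisation (systolic ≥160 or diastolic ≥100) and the secondary endpoint worded as failure to stay below the rescue limits. For HbA1c in the extension, Table 7 and its explanatory text are strict and only the repeat-test instruction is inclusive.

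**5. Does the operator reach the co-primary endpoint?** The plan's own figure reproduces: 25% versus 10%, 181 per arm, two-sided alpha 0.0125, gives 90.0% power. In a simulation on assumed blood pressures (SD 14 mmHg, mean 130 to 136, visit-to-visit correlation 0.5 to 0.7), at most 1.05% of systolic responders change status between the two readings of the 140 mmHg limit. Taking that loss in the dapagliflozin arm alone, 25% × (1 − 0.0105) = 24.74% versus 10%, power is 89.0%. This is deliberately the worst allocation; with arm-specific losses of up to 0.72% on dapagliflozin and 1.05% on placebo, power is 89.9%.

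**The case against.** The best defence is that the haemoglobin slip may never have operated. The g/dL figure comes first, g/L agrees with it, and safety samples go to one central laboratory. If that laboratory reports in g/dL, the wrong figure is never used. The error also runs in the cautious direction: it could exclude a few more anaemic women but admits nobody below 9.0 g/dL. This stands, and it limits the point to a wrong threshold in the text. A reader might infer that women were in fact wrongly excluded; the documents do not say which unit is applied, so that does not follow.

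Timing also counts. The current version adds extension period II for about 600 patients still on drug, and cites web sources accessed in May 2011, against planned enrolment from Q1 2010 over about 8 months. On those dates recruitment was probably over and most week 0 to 24 decisions had been made. This is an inference from planned dates, but it means the correction may change few or no decisions still to come. It does not make the figures right.

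On blood pressure, a reader might infer that a patient exactly at the limit is both forbidden and required to have treatment changed. The protocol does not support that. Both paragraphs also let the investigator alter therapy in the patient's best interest, so a change at the limit is not barred, and the action sentences are consistent with each other. What remains is loose wording.

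Finally, choosing the inclusive form for blood pressure and the strict form for HbA1c is an editorial choice. It follows the weight of the text in each place, but the sponsor could choose otherwise provided that one operator is used throughout.

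**Conclusion.** The women's haemoglobin limit in mmol/L is wrong as written. The correct value is 5.6, from the protocol's own men's pair, and no rounding of that pair rescues 5.9. It leaves a band of about 0.5 g/dL in which eligibility depends on the unit. The two glucose equivalents are also wrong against the protocol's other pairs, by rounding-size amounts; 3.8 mmol/L is still above the 3.5 mmol/L limit for hypoglycaemia. The blood-pressure and HbA1c operators are editorial.

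Overall this is minor. The conversions rest on the documents alone and are firm. The patient counts rest on assumed distributions, and the haemoglobin count further assumes that mmol/L is used throughout; 13 women is the extreme and effectively none is possible. It would be tempting to argue from the non-responder rule that the week-24 results are at risk. The numbers do not support this: even the least favourable case costs one percentage point of power, and sample size, error control and the week-24 conclusions are not materially affected.

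**What to change.** Correct three figures:

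- Exclusion 21, women: <9.0 g/dL (<90 g/L) or <5.6 mmol/L.
- Table 6, weeks 4 to 8: >240 mg/dL (13.3 mmol/L).
- Section 5.6.2.2, after day 7: ≤70 mg/dL (≤3.9 mmol/L).

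Align the wording:

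- Section 5.6.2.4: systolic ≥160 or diastolic ≥100 in every sentence of A, and systolic ≥140 or diastolic ≥95 in every sentence of B.
- Section 5.6.2.1, extension: strictly greater than the HbA1c level for the repeat test, as in Table 7.

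Check which unit and value the central laboratory used for the haemoglobin eligibility limit, and check its glucose and HbA1c alert limits in the same way. The cost is a text correction and that check; design, sample size and analysis stay as they are.
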